**Table 3-3 Study schedule (for subjects completing the treatment phase)**

Category	At end of treatment phase 	Follow-up phase	
Study day		28 days after final dose or on discontinuation 28 or fewer days after final dose 	Follow-up 
Allowable range (days)	-3 to +3	-7 to +7	-
Visit	V f-0	V f-1	V f-n
Pregnancy test 	○ 	○	
Performance Status	○	○	
Vital signs/weight/percutaneous oxygen saturation	○	○	
Chest X-ray	○	○	
12-lead ECG	○ 	○	
Hematology tests, blood biochemistry tests, urinalysis	○	○	
Immunology/hormone tests	○	○	
Serum drug concentration 	○ 	○	
Anti-ONO-4538 antibody 	○ 	○	
Diagnostic imaging (e.g., CT, MRI)	○	○	○
[REDACTED]	[REDACTED]	[REDACTED]	[REDACTED]
	[REDACTED]	[REDACTED]	[REDACTED]
	[REDACTED]		[REDACTED]
Concomitant drugs/adverse events 	←————→		

1. Women of childbearing potential will undergo urine pregnancy testing.
2. Perform only if the subject proceeds to the follow-up phase within 1 year after the start of investigational product administration (by Cycle 9). Collect sample if possible 6 to 12 weeks after the final investigational product dose.

[REDACTED]

[REDACTED]

[REDACTED]

[REDACTED]

5. Investigate all adverse events and concomitant treatments to the completion of the final tests (other than the survey for 'determination of outcome') specified in the protocol. Beyond the completion of the final tests (other than the survey for 'determination of outcome') specified in the protocol, follow any persisting adverse event for which a causal relationship with the investigational product cannot be ruled out, adverse events that resulted in discontinuation, and the concomitant treatments associated with those events until the events resolve, improve, or are determined to be permanent or

no further follow-up is necessary. And all treatment-related adverse events will be followed every 2 weeks if possible.

6. Information from a prior measurement may be included if the day of that measurement falls within the acceptable range at the end of the treatment phase or discontinuation. Unless medically necessary, vital signs will be measured no sooner than 2 days, diagnostic imaging (e.g., CT, MRI) performed no sooner than 15 days, and other tests no sooner than 8 days after the previous measurement.
7. Those subjects who are CR, PR, or SD at the time of discontinuation of the investigational product will undergo follow-up whenever possible with diagnostic imaging and to determine the use and types of any subsequent treatments for non-small cell lung cancer until a subsequent therapy for non-small cell lung cancer is begun or the subject experiences PD or recurrence.
8. Perform only when the test after 28 days of the final investigational product dosage or on discontinuation within 28 days after the final investigational product dosage is not performed due to withdrawal or other reasons. Perform 12-lead ECG also at the discontinuation of treatment phase if the treatment phase is discontinued in Cycle 1 or 4.

### **3.4 Dose and Administration, and Duration of Treatment**

ONO-4538 is administered at a 3 mg/kg dose with a 2-week dosing interval. One cycle consists of 6 weeks. ONO-4538 administration will continue until the development of PD as identified by the investigator or sub investigator according to the RECIST guideline (version 1.1). The appropriate dose of ONO-4538 will be diluted with physiological saline or dextrose 5% in water to a total amount of approximately not less than 60 mL before use (so that the solution drug concentration is no less than 0.35 mg/mL). The entire dose of ONO-4538 will be administered as an intravenous infusion over approximately 60 minutes through a 0.20 ~ 1.20  $\mu$ m in-line filter. The lower limit of the infusion time is 54 minutes. The target upper limit is 90 minutes. At the end of the infusion, the line will be flushed with a sufficient quantity of physiological saline or dextrose 5% in water. The ONO-4538 dose will not be reduced. The administration of ONO-4538 infusion must be completed within 24 hours of preparation. If not used immediately, the infusion solution may be stored under refrigeration condition (2°-8°C, 36°-46°F) for up to 24 hours, and a maximum of 4 hours of the total 24 hours can be at room temperature (20°-25°C, 68°-77°F) and room light. The maximum 4-hour period under room temperature and room light conditions includes the product administration period.

The dose will be changed if the body weight of the subject changes by at least 10% relative to the weight at enrollment. Each subsequent 10% or greater change in body weight is to be handled in a similar manner.

### **3.5 Prior and Concomitant Therapies**

#### **3.5.1 Therapies Prohibited During the Study**

The therapies listed below are prohibited during the study (from the time of informed consent to the completion of the final tests (other than the determination of outcome) specified in the protocol).

1. Immunosuppressants and corticosteroids
2. Anti-cancer agents (e.g., chemotherapy, molecular targeted therapy, immunotherapy)
3. Surgical treatment for a malignant tumor
4. Radiotherapy
5. Radiopharmaceuticals
6. Bisphosphonate products and anti-RANKL antibodies
7. Transplant therapy
8. Any other investigational product

### **3.5.2 Prophylactic Drug Use**

Prophylactic pretreatment with acetaminophen and diphenhydramine before ONO-4538 administration is recommended for subjects who develop an infusion related reaction to a previous dose of ONO-4538.

### **3.6 Investigational Product Discontinuation Criteria**

Subjects satisfying any of the following criteria in the treatment phase will be discontinued the investigational product and proceed to the follow-up phase.

1. The development of PD is identified by the principal or sub investigator according to the RECIST guideline (version 1.1).
2. A worsening of clinical symptoms attributed to disease progression occurs.
3. The subject develops Grade 2 or higher interstitial lung disease, regardless of the causal relationship to the investigational product.
4. Grade 2 or greater eye pain, or visual acuity reduced occurs whose causal relationship with the investigational product cannot be ruled out and does not improve to Grade 1 severity with local treatment.
5. Grade 3 or greater bronchospasm, hypersensitivity reaction, infusion reaction (e.g., pyrexia, chills, nausea, pain, headache, cough, pruritus, rash) or uveitis occurs whose causal relationship with the investigational product cannot be ruled out.
6. An adverse event or other events delay the administration of the investigational product by more than 6 weeks.
7. The investigator or sub investigator otherwise determines that continuing to administer the investigational product is inappropriate due to an efficacy- or safety-related reason.

Even when Criterion 1 is applicable, investigational product treatment may be continued if it is determined through consultation with the sponsor that no worsening of clinical symptoms attributable to disease progression occurs, continued treatment is expected to provide a clinical benefit, and the investigational product can continue to be safely administered. If the investigational product is to be continued, the subject should first be consulted about his or her willingness to continue receiving treatment, and this process should be documented in the medical records. Laboratory tests will be frequently repeated and other measures taken to adequately ensure subject safety. Any subject who is found to have again developed PD according to the RECIST guideline (version 1.1) based on a point

where a decision is made to continue investigational product treatment must cease using the investigational product regardless of whether clinical symptoms have worsened or not.

### **3.7 Sample size determination**

#### **3.7.1 Planned Number of Subjects**

Total of 93 subjects (41 subjects with squamous NSCLC and 52 subjects with non-squamous NSCLC)

#### **3.7.2 Rationale for Number of Subjects**

The objective of the study is to investigate the efficacy of ONO-4538 in patients with stage IIIB/IV or recurrent NSCLC unsuited to radical radiotherapy using centrally assessed response rates as the primary endpoint. The sample size for each histology is calculated in order to confirm anti-tumor response of ONO-4538 in Korean population.

From efficacy data of non-Korean phase I multiple-dose study (CA209003) as of March 18, 2013 ([Table 3-4](#)), the expected response rate for ONO-4538 in patients with squamous NSCLC was set at 23.1% because responses of 22% (4/18) and 24% (5/21) were achieved in patients with squamous NSCLC in the 3 and 10 mg/kg group, respectively. Similarly, the expected response rate for ONO-4538 in patients with non-squamous NSCLC was set at 21.4% because responses of 26% (5/19) and 19% (7/37) were achieved in patients with non-squamous NSCLC in the 3 and 10 mg/kg group, respectively. The threshold response rate (the null hypothesis) was set at 8.8% because the response rate of docetaxel, which was selected as a comparator in non-Korean Phase III studies (CA209017, CA209057), was 8.8% in the phase III trial in patients with NSCLC. Under the assumption of the threshold response rate of 8.8% and the expected response rate of 23.1% and 21.4% for patients with squamous and non-squamous NSCLC respectively, 41 subjects for squamous and 52 subjects for non-squamous will provide a statistical power of at least 80% in a binomial test (normal approximation) with an one-sided significance level of 2.5% (two-sided significance level of 5.0%). The sample sizes (i.e., 41 subjects with squamous NSCLC and 52 subjects with non-squamous NSCLC) were calculated using the formula as follows.

$$N = \left( \frac{z_{1-\alpha} \sqrt{p_0(1-p_0)} + z_{1-\beta} \sqrt{p_1(1-p_1)}}{p_1 - p_0} \right)^2$$

*N*: the number of subjects

*p*0: threshold response rate

*p*1: expected response rate

$z_{1-\alpha}$ :  $(1 - \alpha) \cdot 100$  quantile of the standard normal distribution

$z_{1-\beta}$ :  $(1 - \beta) \cdot 100$  quantile of the standard normal distribution

$\alpha$ : one-sided significance level

$1 - \beta$ : statistical power

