#### **3) FAS**

This set will be defined as a full group of subjects who are included in SAF.

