#### **9.1.4 Analysis Methods**

Response rate (centrally assessed) and its 95% confidence interval (Wilson) will be calculated. The analysis results will be summarized by squamous NSCLC and non-squamous NSCLC separately and totality.

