### 12.2 Significance Level to Be Used

No significance level is defined because no tests will be performed.

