### 14.4 Analysis Methods

- 1) The analysis results will be summarized by squamous NSCLC and non-squamous NSCLC separately and totality.
- 2) Summary statistics and frequency distribution of background factors will be calculated, and classification will be decided.
- 3) The response rate (investigator-assessed) and its 95% confidence interval (Wilson) will be calculated to examine the appropriateness of the analysis method. In addition, missingness will be evaluated as necessary.
- 4) For progression-free survival (investigator-assessed), a Kaplan-Meier curve will be presented. In addition, using the Kaplan-Meier method, the median and its 95% confidence interval and

progression free survival rates at 3 and 6 months and its 95% confidence interval will be estimated for the validation of the analysis methods or handling of data.

- 5) Incidences of adverse events will be calculated. In addition, incidences of adverse events by SOC or by PT will be summarized according to Grade.

The above analyses were performed using the data obtained from 96 subjects treated with the study drug as of Feb. 27, 2015.

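### SAP 3.7.2 claims at least 80% power at one-sided 2.5% in both cohorts; by the exact binomial, squamous power is 76.2% and non-squamous alpha is 3.6%

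*SAP*

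**What the plan says.** SAP 3.7.2 sizes each histology separately. The null is fixed first: "The threshold response rate (the null hypothesis) was set at 8.8" per cent, taken from docetaxel. The expected rates are 23.1% (squamous) and 21.4% (non-squamous). The section then asserts that "41 subjects for squamous and 52 subjects for non-squamous will provide a statistical power of at least 80% in a binomial test (normal approximation"). The level attached to this claim is given as "with an one-sided significance level of 2.5% (two-sided significance level of 5.0" per cent), and the formula used is printed. The section gives no exact power, exact alpha or critical number of responders.

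The primary analysis in SAP 9.1.4 is estimation: "Response rate (centrally assessed) and its 95% confidence interval (Wilson) will be calculated", by histology and overall. SAP 12.2 states: "No significance level is defined because no tests will be performed".

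The denominator is the FAS, defined in SAP 4.1 as everyone in the safety set: "This set will be defined as a full group of subjects who are included in SAF". SAP 14.4 reports "data obtained from 96 subjects treated with the study drug as of Feb. 27, 2015", against 93 planned, without a split by histology.

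**The concern.** Power and alpha are the only rationale given for 41 and 52, and 8.8% is the only reference rate in the plan. Although no test is planned, a reader will naturally hold the Wilson interval up against 8.8% and take the 3.7.2 figures as the error rates of that comparison.

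The normal approximation is weak when few responders are expected under the null. If the true error rates differ from those stated, a squamous cohort that responds as hoped will fail to exclude 8.8% more often than the plan implies. A non-squamous cohort no better than docetaxel will appear to exclude it more often than the plan implies.

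**Working it through.** **Inputs (all SAP 3.7.2).** p0 = 0.088; p1 = 0.231 (squamous), 0.214 (non-squamous); one-sided alpha 0.025 (z = 1.960); power 0.80 (z = 0.842); n = 41 and 52.

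**1. Reproduce the plan's figures.** N = [(1.960·√(p0(1−p0)) + 0.842·√(p1(1−p1))) / (p1−p0)]², with √(0.088·0.912) = 0.2833.

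- Squamous: √(0.231·0.769) = 0.4215; N = [(0.5552 + 0.3547)/0.143]² = 40.49, rounded up to 41.
- Non-squamous: √(0.214·0.786) = 0.4101; N = [(0.5552 + 0.3452)/0.126]² = 51.07, rounded up to 52.

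Inverting the formula, approximate power = Φ[((p1−p0)√n − 0.5552)/√(p1(1−p1))], which is 80.4% at n = 41 and 80.6% at n = 52. The stated sizes reproduce.

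**2. Expected responders at 8.8%.** 41 × 0.088 = 3.6; 52 × 0.088 = 4.6.

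**3. Smallest count that excludes 8.8%.** Score statistic z = (x/n − p0)/√(p0(1−p0)/n), critical value 1.96, alongside the Wilson 95% lower limit:

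| Count | z | Wilson lower limit |
|---|---|---|
| 7/41 | 1.87 | 8.53% |
| 8/41 | 2.42 | 10.23% |
| 8/52 | 1.68 | 8.01% |
| 9/52 | 2.17 | 9.38% |

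The normal-approximation test and the planned interval both cross 8.8% at 8/41 and 9/52.

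**4. Exact binomial probability of reaching those counts.**

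| Cohort and count | Alpha: P(X ≥ count) at 8.8% | Power: P(X ≥ count) at p1 |
|---|---|---|
| Squamous, 8/41 | 2.47% | 76.2% |
| Non-squamous, 9/52 | 3.63% | 81.1% |
| Non-squamous, 10/52 | 1.42% | 70.1% |

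Squamous power is 80 − 76.2 = 3.8 points short. Non-squamous alpha is 3.63 − 2.5 = 1.1 points over. Relaxing squamous to 7/41 would give power 86.7% but alpha 6.5%.

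**5. Sensitivity to the 96 treated.** The split is not given. Assume each cohort reached at least its planned size. The thresholds stay at 8 and 9 responders:

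| Split (squamous/non-squamous) | Squamous alpha, power | Non-squamous alpha, power |
|---|---|---|
| 41/55 | 2.5%, 76.2% | 5.0%, 86.0% |
| 42/54 | 2.8%, 78.6% | 4.5%, 84.5% |
| 43/53 | 3.2%, 80.9% | 4.1%, 82.9% |
| 44/52 | 3.6%, 82.9% | 3.6%, 81.1% |

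The squamous power shortfall disappears at 43 or more. Non-squamous alpha exceeds 2.5% at every split shown.

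**The case against.** The strongest reply is that the SAP says what it did: it labels the calculation a normal approximation, prints the formula, and gets the arithmetic right. That stands as a defence of how N was derived. It does not make the power and alpha true of the test, because the response count is binomial whatever formula was used to choose n.

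Second, SAP 12.2 rules out testing and no section defines success as a lower limit above 8.8%. That also stands, and it limits the consequence: no declared decision is affected. But 3.7.2 itself names a null hypothesis, a significance level and a power, and gives confirming anti-tumour response as the purpose of the sizing, so comparing the interval with 8.8% is the obvious reading.

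Third, the 3.6% depends on the rule. A continuity-corrected or exact rule needs 10/52, which brings alpha to 1.4% but power down to 70.1%. Either way n = 52 does not give both properties. Squamous does not depend on the rule: score, continuity-corrected, Wilson and exact versions all give 8/41.

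Fourth, the figures move in a sawtooth with n and the actual sizes differ from plan. If squamous fell one short of plan (40/56), non-squamous would need 10/56, with alpha 2.3% and power 78.8%. This is a fair reason to recompute at the actual sizes, not to keep the present sentence.

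Fifth, the gap is small beside the uncertainty in the expected rates, which rest on 9/39 and 12/56. At n = 41, exact power runs from 71.8% at a true rate of 22.2% to 80.1% at 24%. True, but the claim in 3.7.2 is made at 23.1% and is not met there.

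**Conclusion.** The concern holds. At the planned sizes the design does not deliver the stated pair of properties in either cohort: squamous has exact power 76.2% against at least 80%, and non-squamous has exact one-sided alpha 3.6% against 2.5%. A squamous cohort with a true rate of 23.1% fails to exclude 8.8% about 24% of the time, not at most 20%.

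This rests on the SAP's own p0 and p1, the planned 41 and 52, and reading the Wilson lower limit (equivalently the uncorrected normal-approximation test) against 8.8%. It is not an arithmetic error, and it leaves the sample, the response-rate estimate and the interval untouched. It should be fixed because it misstates the only rationale given for the cohort sizes.

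**What to change.** Keep both sample sizes and replace the power sentence in SAP 3.7.2 with:

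> The sizes 41 and 52 come from the normal-approximation formula (approximate power 80.4% and 80.6% at a nominal one-sided 2.5%). By the exact binomial distribution, the smallest counts whose Wilson 95% lower limit exceeds 8.8% are 8/41 and 9/52. For squamous, the probability of reaching the count is 2.5% at a true rate of 8.8% and 76.2% at 23.1%. For non-squamous, it is 3.6% at 8.8% and 81.1% at 21.4%. These counts are descriptive; no test is performed (see 12.2).

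This removes 80% power at 2.5% as a claimed property of both cohorts. Then recompute the two counts and their probabilities for the FAS number in each histology, since 96 subjects were treated. No success rule and no extra patients are proposed.

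The cost is SAP wording only. The stated squamous power and non-squamous alpha become slightly less favourable; data collection, estimates and intervals do not change.

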## **9 EFFICACY EVALUATION**

### **9.1 Primary Efficacy Analysis**

#### **9.1.1 Objective**

To confirm the efficacy of ONO-4538 in stage IIIB/IV or recurrent NSCLC unsuited to radical radiotherapy and resistant to a platinum-based chemotherapeutic regimen using the response rate assessed by the central imaging analysis facility (centrally assessed) as the primary efficacy endpoint.

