## 16 SAS PROCEDURE FOR ANALYSIS

### 16.1 95% confidence interval (Wilson)

```
PROC FREQ DATA=[Analysis data set];  
  TABLES [Binary data] / BINOMIAL(WILSON) alpha=0.05;  
  BY [Histologic type];  
RUN;
```

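### At the planned sizes the Wilson rule implied by SAP 3.7.2 has 76.2% exact power in squamous and 3.63% exact one-sided error in non-squamous, and SAP 9.1.4 and 12.2 do not carry the 8.8% criterion through

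*SAP*

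**What the plan says.** SAP 3.7.2 gives the purpose of the sizing: "The sample size for each histology is calculated in order to confirm anti-tumor response of ONO-4538 in Korean population". It sets a null response rate of 8.8%, expected rates of 23.1% (squamous) and 21.4% (non-squamous), and sample sizes of 41 and 52. It says that these "will provide a statistical power of at least 80% in a binomial test (normal approximation) with an one-sided significance level of 2.5" per cent, equivalent to 5.0% two-sided. SAP 9.1.1 words the primary objective in the same spirit: "To confirm the efficacy of ONO-4538 in stage IIIB/IV or recurrent NSCLC unsuited to radical radiotherapy".

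The primary analysis in SAP 9.1.4 is: "Response rate (centrally assessed) and its 95% confidence interval (Wilson) will be calculated". On presentation it adds: "The analysis results will be summarized by squamous NSCLC and non-squamous NSCLC separately and totality". The code in SAP 16.1 is "TABLES [Binary data] / BINOMIAL(WILSON) alpha=0.05", run by histologic type, with no null proportion. In the current SAP text, 8.8% appears only in 3.7.2.

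SAP 12.2 states: "No significance level is defined because no tests will be performed".

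**The concern.** Section 3.7.2 describes a hypothesis-testing design with a null, a level and a power for each histology. Section 12.2 says that no test is done and no level exists. Section 9.1.4 sits between them: it plans an interval that could serve as the test but does not say that it does, or that 8.8% is the value to compare it with. A reader of the final report has to infer what *confirm* means.

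The second issue is whether the stated 80% and 2.5% describe the rule that the plan implies. With about 40 to 50 subjects and a null rate under 10%, the response count is coarse and skewed, so a normal approximation can be off by several points. If so, the SAP quotes a power and an error rate that the design does not have.

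**Working it through.** **Inputs (all SAP 3.7.2).** p0 = 0.088; p1 = 0.231 (squamous) and 0.214 (non-squamous); one-sided α = 0.025 (z = 1.960); power 0.80 (z = 0.8416); n = 41 and 52.

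**1. Reproduce the plan's sample sizes.** N = [(z(1−α)·√(p0(1−p0)) + z(1−β)·√(p1(1−p1))) / (p1 − p0)]², with √(0.088 × 0.912) = 0.2833.

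- Squamous: √(0.231 × 0.769) = 0.4215. N = [(1.960 × 0.2833 + 0.8416 × 0.4215) / 0.143]² = 40.49, rounded up to 41.
- Non-squamous: √(0.214 × 0.786) = 0.4101. N = [(1.960 × 0.2833 + 0.8416 × 0.4101) / 0.126]² = 51.07, rounded up to 52.

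Both agree with the SAP. Approximate power is Φ{[(p1 − p0)√n − z(1−α)√(p0(1−p0))] / √(p1(1−p1))}, which gives 80.4% at n = 41 and 80.6% at n = 52. The statement in 3.7.2 is true as an approximation.

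**2. Show that the planned interval is the sizing test.** The sizing test rejects when the responder count exceeds n·p0 + 1.960·√(n·p0(1−p0)).

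- n = 41: 3.608 + 1.960 × 1.814 = 7.16, so at least 8 responders.
- n = 52: 4.576 + 1.960 × 2.043 = 8.58, so at least 9 responders.

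The 95% Wilson lower limits give the same cut-offs: 7/41 → 8.53% and 8/41 → 10.23%; 8/52 → 8.01% and 9/52 → 9.38%. The interval in 9.1.4 therefore carries the 3.7.2 test once it is compared with 8.8%.

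**3. Exact properties of that rule.** With X binomial, error is P(X ≥ r | n, p0) and power is P(X ≥ r | n, p1).

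| | Rule | Exact one-sided error (stated 2.5%) | Exact power (stated at least 80%) |
|---|---|---|---|
| Squamous | ≥8/41 | 2.47% | 76.2% |
| Non-squamous | ≥9/52 | 3.63% | 81.1% |

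Squamous keeps the level and misses the power by 80 − 76.2 = 3.8 points. Non-squamous keeps the power and exceeds the level by 3.63 − 2.5 = 1.13 points.

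**4. Comparison with an exact 2.5% test.** In squamous the cut-off is unchanged (8/41). In non-squamous it rises to 10/52, with error 1.42% and power 70.1%. A result of 9/52 would pass the Wilson comparison and fail an exact test, so the choice of rule can decide the conclusion.

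**5. The text.** Section 3.7.2 has a null, a level and a power. Section 9.1.4 has an interval and no reference value. Section 12.2 has no test and no level. As worded, 3.7.2 and 12.2 cannot both describe the primary analysis.

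**The case against.** The strongest reply is that 3.7.2 claims its power only under a normal approximation, and under that approximation the claim is correct. This stands: there is no arithmetic error and the approximation is disclosed. It does not settle the matter, because the quoted 80% and 2.5% will be read as properties of the trial, and the exact binomial figures for the same rule are different.

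A second reply is that this is an uncontrolled Phase II study whose overall objective (SAP section 2) is to investigate efficacy and safety, so sizing on a test and reporting an interval is a normal estimation plan. That is a legitimate design, but it does not fit the word *confirm* in 3.7.2 and 9.1.1. One side of the text has to move.

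A reader might go further and infer that the report may claim success from any of the squamous, non-squamous or total intervals, with an inflated joint error or a reduced joint power. The documents do not support this. Null, expected rate, level and sample size are all set per histology, the code in 16.1 runs by histologic type, and the total has no expected rate or power of its own. No section makes an either-or or a both-must-pass claim, so joint figures would answer a question that the plan does not ask. Presentation by histology and in total recurs throughout the SAP as a reporting convention.

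A reader might also infer that the threshold was picked after data were seen. The revision history points the other way: the text of 3.7.2 that version 2.0 replaced already carried 8.8% and both expected rates, and version 2.0 is where changes reflecting the data review were made.

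**Conclusion.** The concern holds in limited form. The sample sizes are right, and the Wilson interval is a suitable vehicle for the design test. What needs correcting is that the stated level and power are approximate, that neither histology has both when computed exactly (squamous 2.47% and 76.2%; non-squamous 3.63% and 81.1%), that 12.2 conflicts with 3.7.2, and that nothing in the SAP ties the interval in 9.1.4 to 8.8%. The importance is minor to moderate.

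The exact figures assume the planned 41 and 52, the SAP's own p0 and p1, and the rule that the Wilson lower limit exceeds 8.8%. They will change with the full analysis set actually reached. SAP 14.4 reports 96 treated subjects without a histology split, so they cannot be updated from these documents.

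The protocol supplied is a synopsis with no statistics section. The absence of a decision rule is therefore established for the SAP only; it would be too strong to say that the trial never had one.

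**What to change.** First check the statistics section of the full protocol. If it states a decision rule, copy that rule into SAP 9.1.4. If it does not, keep the sample size and the interval and make these wording changes:

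- **3.7.2:** label 80% and 2.5% as approximate and put the exact values beside them (n = 41: error 2.47%, power 76.2%; n = 52: error 3.63%, power 81.1%). Recompute them for the full analysis set reached in each histology.
- **9.1.4:** state that, in each histology separately as it was sized, the lower limit of the 95% Wilson interval is compared with 8.8%, and that the total is descriptive.
- **12.2:** say that no test is made beyond this comparison.
- **Revision history:** disclose that the 8.8% threshold predates SAP version 2.0 but that the written criterion followed the 2015 data review. That review covered investigator-assessed response, and SAP 14.4 records of its analyses: "The above analyses were performed using the data obtained from 96 subjects treated with the study drug as of Feb. 27, 2015".

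An equally valid alternative is to leave 12.2 as it is and reword 3.7.2 and 9.1.1 as estimation, with no confirmatory claim.

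Neither route needs more subjects or data. The cost of the first is that the stated figures become slightly less favourable, including an acknowledged 3.63% error in non-squamous. Holding 2.5% exactly there (at least 10/52) would instead lower power from 81.1% to 70.1%.
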